7.7.3 Permitted Therapy

Participants are permitted the use of topical, ocular, intra-articular, intranasal, and inhalational corticosteroids (with minimal systemic absorption). Adrenal replacement steroid doses > 10 mg daily prednisone are permitted. A brief (less than 3 weeks) course of corticosteroids for prophylaxis (eg, contrast dye allergy) or for treatment of non-autoimmune conditions (eg, delayed-type hypersensitivity reaction caused by a contact allergen) is permitted.

7.8 Treatment After the End of the Study

At the end of the study, BMS will not continue to provide BMS supplied study treatment to participants/investigators unless BMS chooses to extend the study. The investigator should ensure that the participant receives appropriate standard of care to treat the condition under study.

BMS reserves the right to terminate access to BMS supplied study treatment if any of the following occur: a) the study is terminated due to safety concerns; b) the development of nivolumab and/or ipilimumab is terminated for other reasons, including but not limited to lack of efficacy and/or not meeting the study objectives; c) the participant can obtain medication from a government sponsored or private health program. In all cases BMS will follow local regulations.

8 DISCONTINUATION CRITERIA

8.1 Discontinuation from Study Treatment

Participants **MUST** discontinue investigational product (and non-investigational product at the discretion of the investigator) for any of the following reasons:

- Participant's request to stop study treatment. Participants who request to discontinue study treatment will remain in the study and must continue to be followed for protocol specified follow-up procedures. The only exception to this is when a participant specifically withdraws consent for any further contact with him/her or persons previously authorized by participant to provide this information
- Any clinical AE, laboratory abnormality or intercurrent illness which, in the opinion of the investigator, indicates that continued participation in the study is not in the best interest of the participant
- Termination of the study by BMS
- Loss of ability to freely provide consent through imprisonment or involuntarily incarceration for treatment of either a psychiatric or physical (eg, infectious disease) illness

The assessment for discontinuation of nivolumab should be made separately from the assessment made for discontinuation of ipilimumab. Although there is overlap among the discontinuation criteria, if discontinuation criteria are met for ipilimumab but not for nivolumab, treatment with nivolumab may continue if ipilimumab is discontinued.

If a participant in any of the nivolumab/ipilimumab combination arms meets criteria for discontinuation and investigator is unable to determine whether the event is related to both or one study drug, the participant should discontinue both nivolumab and ipilimumab and be taken off the treatment phase of the study.

8.1.1 Study Drug Discontinuation

8.1.1.1 Nivolumab Discontinuation for Cohorts A, B, and C

Nivolumab treatment should be permanently discontinued for the following:

- Any Grade 2 drug-related uveitis, eye pain or blurred vision that does not respond to topical therapy and does not improve to Grade 1 severity within the re-treatment period OR requires systemic treatment
- Any Grade 3 non-skin, drug-related AE lasting > 7 days, or recurs with the following exceptions for laboratory abnormalities, diarrhea, colitis, neurologic toxicity, drug-related uveitis, pneumonitis, bronchospasm, hypersensitivity reactions, infusion reactions, and endocrinopathies:
 - Grade 3 drug-related diarrhea, colitis, neurologic toxicity, uveitis, pneumonitis, bronchospasm, myocarditis, hypersensitivity reaction, or infusion reaction of any duration requires discontinuation

- Grade 3 drug-related endocrinopathies, adequately controlled with only physiologic hormone replacement do not require discontinuation. Adrenal insufficiency requires discontinuation regardless of control with hormone replacement.
- Grade 3 drug-related laboratory abnormalities do not require treatment discontinuation except:
 - ◆ Grade 3 drug-related thrombocytopenia > 7 days or associated with bleeding requires discontinuation
 - ◆ Any drug-related liver function test (LFT) abnormality that meets the following criteria require discontinuation:
 - Grade ≥ 3 drug-related AST, ALT or Total Bilirubin requires discontinuation*
 - Concurrent AST or ALT > 3 x ULN and total bilirubin > 2x ULN

*In most cases of Grade 3 AST or ALT elevation, study treatment will be permanently discontinued. If the investigator determines a possible favorable benefit/risk ratio that warrants continuation of study treatment, a discussion between the investigator and the BMS Medical Monitor/designee must occur.

- Any Grade 4 drug-related adverse event or laboratory abnormality (including but not limited to creatinine, AST, ALT, or Total Bilirubin), except for the following events which do not require discontinuation:
 - Grade 4 neutropenia ≤ 7 days
 - Grade 4 lymphopenia or leukopenia or asymptomatic amylase or lipase
 - Isolated Grade 4 electrolyte imbalances/abnormalities that are not associated with clinical sequelae and are corrected with supplementation/appropriate management within 72 hours of their onset
 - Grade 4 drug-related endocrinopathy adverse events, such as, hyper- or hypothyroidism, or glucose intolerance, which resolve or are adequately controlled with physiologic hormone replacement (corticosteroids, thyroid hormones) or glucose-controlling agents, respectively, may not require discontinuation after discussion with and approval from the BMS Medical Monitor.
- Any event that leads to delay in dosing lasting > 6 weeks for nivolumab from the previous dose requires discontinuation, with the following exceptions:
 - Dosing delays to allow for prolonged steroid tapers to manage drug-related adverse events are allowed.
 - Dosing delays lasting > 6 weeks for nivolumab from the previous dose that occur for non-drug-related reasons may be allowed if approved by the BMS Medical Monitor (or designee).

Prior to re-initiating treatment in a participant with a dosing delay lasting > 6 weeks, the BMS Medical Monitor (or designee) must be consulted. Tumor assessments should continue as per protocol even if dosing is delayed. Periodic study visits to assess safety and laboratory studies

should also continue every 6 weeks or more frequently if clinically indicated during such dosing delays.

Any adverse event, laboratory abnormality, or intercurrent illness which, in the judgment of the Investigator, presents a substantial clinical risk to the participant with continued nivolumab dosing.

The assessment for discontinuation of nivolumab should be made separately from the assessment made for discontinuation of ipilimumab. Although there is overlap among the discontinuation criteria, if discontinuation criteria are met for ipilimumab but not for nivolumab, treatment with nivolumab may continue if ipilimumab is discontinued.

If a participant meets criteria for discontinuation and investigator is unable to determine whether the event is related to both or one study drug, the participant should discontinue both nivolumab and ipilimumab and be taken off the treatment phase of the study. Continuation of ipilimumab after discontinuation of nivolumab is not allowed on study.

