7.4 Dosage Modification

7.4.1 Dose Delay Criteria for Cohorts A, B, and C

Nivolumab and ipilimumab administration should be delayed for the following:

- Grade 2 non-skin, drug-related AE, except for fatigue
- Grade 3 skin, drug-related AE
- Grade 2 drug-related creatinine, AST, ALT and/or total bilirubin abnormalities
- Grade ≥ 3 drug-related laboratory abnormality, with the following exceptions:
 - Grade 3 lymphopenia or asymptomatic amylase or lipase does not require a dose delay
 - Grade ≥ 3 AST, ALT, Total Bilirubin will require dose discontinuation
- Any AE, laboratory abnormality or inter-current illness which, in the judgment of the investigator, warrants delaying the dose of study medication.
- Participants receiving ipilimumab in combination with nivolumab that have drug-related toxicities that meet the criteria for dose delay, should have both drugs (ipilimumab and nivolumab) delayed until retreatment criteria are met. (Exceptions apply to the retreatment criteria after dose delay of ipilimumab and nivolumab for Grade 4 amylase and lipase abnormalities that are not associated with symptoms or clinical manifestations of pancreatitis and that are attributed to ipilimumab alone.)

Participants who require delay should be re-evaluated weekly or more frequently if clinically indicated and resume study medication dosing when re-treatment criteria are met.

Rescheduling:

- Nivolumab may be delayed until the next planned ipilimumab dose if the next ipilimumab dose is scheduled within the next 12 days. This will permit periodic ipilimumab dosing to be synchronized with nivolumab dosing.

- Ipilimumab should be dosed at the specified interval regardless of any delays in intervening nivolumab doses. However, in order to maintain periodic synchronized dosing of ipilimumab and nivolumab, the dosing days of nivolumab and ipilimumab may be adjusted within the permitted ± 5 day window, as long as consecutive nivolumab doses are given at least 12 days apart. Ipilimumab may be delayed beyond the 5 day window if needed to synchronize with the next nivolumab dose.
- If an ipilimumab dose is delayed beyond 6 weeks from the prior ipilimumab dose, then subsequent ipilimumab doses should be rescheduled to maintain the 6 week interval between consecutive ipilimumab doses.
- A dose delay of ipilimumab which results in no ipilimumab dosing for > 12 weeks requires ipilimumab discontinuation, with exceptions as noted in [Section 8.1.1.2](#).

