7.4.5 Criteria to Resume Dosing

7.4.5.1 Criteria to Resume Nivolumab for Cohorts A, B, and C

Participants may resume treatment with nivolumab when the drug-related AE(s) resolve(s) to Grade \leq 1 or baseline, with the following exceptions:

- Participants may resume treatment in the presence of Grade 2 fatigue.
- Participants who have not experienced a Grade 3 drug-related skin AE may resume treatment in the presence of Grade 2 skin toxicity.
- Participants with baseline Grade 1 AST/ALT or total bilirubin who require dose delays for reasons other than a 2-grade shift in AST/ALT or total bilirubin may resume treatment in the presence of Grade 2 AST/ALT OR total bilirubin.
- Participants with combined Grade 2 AST/ALT and total bilirubin values meeting discontinuation parameters ([Section 8.1](#)) should have treatment permanently discontinued.
- Drug-related pulmonary toxicity, diarrhea, or colitis must have resolved to baseline before treatment is resumed. Participants with persistent Grade 1 pneumonitis after completion of a

steroid taper over at least 1 month may be eligible for retreatment if discussed with and approved by the BMS Medical Monitor.

- Participants who received systemic corticosteroids for management of any drug-related toxicity must be off corticosteroids or have tapered down to an equivalent dose of prednisone ≤ 10 mg/day.

Participants with drug-related endocrinopathies adequately controlled with only physiologic hormone replacement may resume treatment after consultation with the BMS Medical Monitor (or designee). Adrenal insufficiency requires discontinuation regardless of control with hormone replacement.

Dose delay of nivolumab which results in treatment interruption of > 6 weeks requires treatment discontinuation, with exceptions as noted in [Section 8.1.1](#).

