7.4.5.2 Criteria to Resume Ipilimumab for Cohorts A, B, and C

Participants may resume treatment with nivolumab and ipilimumab when drug-related AE(s) resolve(s) to Grade 1 or baseline value, with the following exceptions:

- Participants may resume treatment in the presence of Grade 2 fatigue.
- Participants who have not experienced a Grade 3 drug-related skin AE may resume treatment in the presence of Grade 2 skin toxicity.
- Participants with baseline Grade 1 AST/ALT or total bilirubin who require dose delays for reasons other than a 2-grade shift in AST/ALT or total bilirubin may resume treatment in the presence of Grade 2 AST/ALT or total bilirubin.
- Participants with combined Grade 2 AST/ALT and total bilirubin values meeting discontinuation parameters ([Section 8.1](#)) should have treatment permanently discontinued.
- Drug-related pulmonary toxicity, diarrhea, or colitis must have resolved to baseline before treatment is resumed.
- Participants who received systemic corticosteroids for management of any drug-related toxicity must be off corticosteroids or have tapered down to an equivalent dose of prednisone ≤ 10 mg/day.
- Drug-related endocrinopathies (except Grade 3 or greater adrenal insufficiency) adequately controlled with only physiologic hormone replacement may resume treatment after consultation with the BMS Medical Monitor
- Dose delay of ipilimumab which results in no ipilimumab dosing for > 12 weeks requires ipilimumab discontinuation, with exceptions as noted in [Section 8.1.1.2](#).
- Ipilimumab may not be resumed sooner than 37 days after the prior ipilimumab dose.
- In general, participants who meet criteria to resume ipilimumab will also have met criteria to resume nivolumab, so it should be feasible to synchronize dosing of both drugs when resuming ipilimumab. In order to facilitate this, the dosing days of nivolumab and ipilimumab may be adjusted within the permitted ± 5 day window, as long as consecutive nivolumab doses are given at least 12 days apart.

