One exception to note is when ipilimumab and nivolumab doses are delayed due to drug-related Grade 4 amylase or lipase abnormalities not associated with symptoms or clinical manifestations of pancreatitis. If the investigator assesses the Grade 4 amylase or lipase abnormality to be related to ipilimumab and not related to nivolumab, nivolumab may be resumed when the amylase or lipase abnormality resolves to Grade ≤ 3 but ipilimumab may only be resumed when the amylase or lipase abnormality resolves to Grade 1 or baseline. Investigator attribution of this toxicity to the ipilimumab dosing must be clearly noted in the participant's medical chart. The BMS Medical Monitor should be consulted prior to resuming nivolumab in such participants.

See [Section 8](#) for treatment discontinuation criteria.

Please see [Section 7.4.5.3](#) Criteria to Resume Nivolumab or Ipilimumab for Special Population.

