Patients on IV steroids may be switched to an equivalent dose of oral corticosteroids (e.g. prednisone) at start of tapering or earlier, once sustained clinical improvement is observed. Lower bioavailability of oral corticosteroids should be taken into account when switching to the equivalent dose of oral corticosteroids

27-Jun-2018

Hepatic Adverse Event Management Algorithm

Rule out non-inflammatory causes. If non-inflammatory cause, treat accordingly and continue I-O therapy. Consider imaging for obstruction.

[figure not shown]
Patients on IV steroids may be switched to an equivalent dose of oral corticosteroids (e.g. prednisone) at start of tapering or earlier, once sustained clinical improvement is observed. Lower bioavailability of oral corticosteroids should be taken into account when switching to the equivalent dose of oral corticosteroids.

*The recommended starting dose for grade 4 hepatitis is 2 mg/kg/day methylprednisolone IV.

27-Jun-2018

Endocrinopathy Adverse Event Management Algorithm

Rule out non-inflammatory causes. If non-inflammatory cause, treat accordingly and continue I-O therapy. Consider visual field testing, endocrinology consultation, and imaging.

[figure not shown]

Patients on IV steroids may be switched to an equivalent dose of oral corticosteroids (e.g. prednisone) at start of tapering or earlier, once sustained clinical improvement is observed. Lower bioavailability of oral corticosteroids should be taken into account when switching to the equivalent dose of oral corticosteroids.

27-Jun-2018

Skin Adverse Event Management Algorithm

Rule out non-inflammatory causes. If non-inflammatory cause, treat accordingly and continue I-O therapy.

Patients on IV steroids may be switched to an equivalent dose of oral corticosteroids (e.g. prednisone) at start of tapering or earlier, once sustained clinical improvement is observed. Lower bioavailability of oral corticosteroids should be taken into account when switching to the equivalent dose of oral corticosteroids.

[figure not shown]
*Refer to NCI CTCAE v4 for term-specific grading criteria.

**If SJS/TEN is suspected, withhold I-O therapy and refer patient for specialized care for assessment and treatment. If SJS or TEN is diagnosed, permanently discontinue I-O therapy.

27-Jun-2018

Neurological Adverse Event Management Algorithm

[figure not shown]
Rule out non-inflammatory causes. If non-inflammatory cause, treat accordingly and continue I-O therapy.

[figure not shown]

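### If an SJS or TEN event is graded 3, the dosing rules in Sections 7 and 8 delay treatment and allow it to resume, while the Appendix 8 skin algorithm stops it permanently; Section 8 should carry that stop.

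*Combined protocol and SAP*

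**What the plan says.** **Delay.** Section 7.4.1 lists "Grade 3 skin, drug-related AE" among the reasons to delay both drugs. Delayed participants are re-evaluated and should "resume study medication dosing when re-treatment criteria are met".

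**Resume.** Section 7.4.5.1 states: "Participants may resume treatment with nivolumab when the drug-related AE(s) resolve(s) to Grade" 1 or lower, or baseline. Section 7.4.5.2 states: "Participants may resume treatment with nivolumab and ipilimumab when drug-related AE(s) resolve(s) to Grade 1 or baseline value". In both sections the only exception about skin toxicity concerns resuming at Grade 2, which is open only to participants with no Grade 3 drug-related skin event. Section 7.4.5.2 ends by sending the reader to Section 8 "for treatment discontinuation criteria".

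**Discontinue.** The general Grade 3 stop for nivolumab (8.1.1.1) reads "Any Grade 3 non-skin, drug-related AE lasting > 7 days, or recurs with the following exceptions". The one for ipilimumab (8.1.1.2) also covers non-skin events only. Grade 4 drug-related events stop both drugs, and none of the listed Grade 4 exceptions is a skin event. SJS and TEN appear in neither list. Cohort A1 inherits these rules through 7.4.1.1, 7.4.5.3 and 8.1.1.3, with exceptions for hepatic and renal matters only.

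**Appendix 8, skin algorithm.** A footnote says to withhold treatment and refer the patient when SJS/TEN is suspected, and then: "If SJS or TEN is diagnosed, permanently discontinue I-O therapy". It sets no grade threshold. For grading, the algorithm says "Refer to NCI CTCAE v4 for term-specific grading criteria".

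**The concern.** The sponsor has already decided that a diagnosis of SJS or TEN ends immuno-oncology treatment. That decision stands only in a footnote to an appendix. The sections that a site works through when deciding whether to delay, restart or stop do not contain it. Read alone, they lead from a Grade 3 skin event to a delay and then to permitted re-dosing with both drugs.

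What is at stake is participant safety: re-exposure after a diagnosis for which the sponsor's own algorithm requires a permanent stop. The primary endpoint and the analyses are not affected.

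**Working it through.** The plan gives no figure on this point, so the check is mainly a comparison of texts, followed by a bounded illustration of size.

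**Step 1. Follow one case through both texts.** Take a diagnosed, drug-related SJS event (or TEN, if so graded).

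| Grade | Sections 7.4.1, 7.4.5, 8.1.1 | Appendix 8 footnote |
|---|---|---|
| 4 | Permanent stop, both drugs | Permanent stop |
| 3 | Delay; may resume at Grade 1 or baseline | Permanent stop |

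The texts agree at Grade 4 and differ at Grade 3. Nothing is claimed below Grade 3.

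**Step 2. Is resumption after a Grade 3 skin event really open?** Yes. A previous Grade 3 skin event removes only the allowance to resume at Grade 2. Resumption at Grade 1 or baseline remains.

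**Step 3. Does any text say which rule prevails?** None was found for skin. Appendix 8 describes itself as guidance to the investigator. The only ranking found is in 8.1.3, for liver tests: stopping is to be considered under the appendix conditions and is required under Section 8.1. Section 7.4.4 sends sites to Appendix 7 for the algorithms, but Appendix 7 is the German HIV amendment. The same wrong number appears in 8.1.3 and in Section 9 (pulmonary algorithm). The table of contents lists Appendix 8 correctly.

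**Step 4. Do other rules close the gap?**
- Investigator-judgement stops (8.1, 8.1.1.1, 8.1.1.2) bind once the judgement is made, but leave that judgement to the site.
- The Grade 3 hypersensitivity stops apply only if SJS/TEN is read as hypersensitivity. The documents place it under skin, and in 8.1.1.1 this stop sits inside the non-skin bullet.
- Delay limits (> 6 weeks nivolumab, > 12 weeks ipilimumab) make exceptions for prolonged steroid tapers. Restarting after such a delay requires Medical Monitor consultation; a shorter delay does not trigger it.
- Section 9 requires immediate safety concerns to be discussed with the sponsor to decide whether treatment continues.

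Each lowers the chance of re-treatment. None is an SJS/TEN-specific stop.

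**Step 5. Size.** Planned treated participants: 400 (A) + 400 (B) + 200 (A1) + 100 (C) = 1,100.

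Section 3.2.4 reports at most 5% Grade 3/4 treatment-related select events per category on this schedule, in 39 participants. That gives 0.05 × 1,100 = 55 skin events. Since 5% of 39 is about 2, the exact 95% interval for 2/39 is 0.6% to 17.3%, or about 7 to 191 of 1,100. This counts all Grade 3/4 skin events, including Grade 4, so it does not estimate SJS/TEN.

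For SJS/TEN the inputs must be assumed; neither is in the documents. Let p be the incidence of Grade 3 SJS/TEN and q the share re-treated. Expected re-treatments are 1,100 × p × q, and the chance of at least one is 1 − (1 − pq)^1100.

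| p (assumed) | q (assumed) | Expected events | Expected re-treatments | Chance of at least one |
|---|---|---|---|---|
| 0.01% | 5% | 0.11 | 0.0055 | 0.5% |
| 0.01% | 50% | 0.11 | 0.055 | 5.4% |
| 0.1% | 5% | 1.1 | 0.055 | 5.4% |
| 0.1% | 50% | 1.1 | 0.55 | 42.3% |

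**The case against.** The strongest reply is that there is no contradiction. The resume rules grant a permission, while the footnote is specific and unqualified. A site that stops obeys every sentence, and no text authorises a restart after diagnosed SJS. Section 7.4.4 also says the algorithms are in both Investigator Brochures.

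A restart would also have to get past the sponsor. Besides the Section 9 discussion and the Medical Monitor consultation, serious events are reported within 24 hours (9.2.1) and reviewed by the sponsor in real time (5.1.2). The claim also needs a Grade 3 grading that the documents do not show, because CTCAE v4, the skin flowchart and the Brochures are not visible here.

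Most of this stands. It rules out a stronger reading that a reader might infer, namely that the protocol orders re-dosing after SJS or that the two texts cannot both be followed. The wording of 7.4.1 about resuming depends on re-treatment criteria, and those criteria only permit.

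What the reply does not supply is a sentence making the footnote prevail, or a stop in Section 8, where the resume text sends the site. Section 8.1.1.1 does name other specific events, such as Grade 3 myocarditis and adrenal insufficiency. Myocarditis appears in both 7.4.4 and 8.1.1.1; SJS/TEN did not get the same treatment. The sponsor checks are real, but they call for discussion or review and do not require a stop.

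**Conclusion.** The point holds as a conditional gap in participant-safety rules. If a drug-related SJS or TEN event is graded 3, the rules in Sections 7 and 8 allow what the Appendix 8 algorithm forbids, and the documents do not say which governs. It should be corrected at the next revision. The safeguards and the expected rarity keep it from being more urgent.

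The verdict assumes that at least one of the two conditions can be graded 3; if neither can, the texts agree for every graded case considered here. The size is unknown. The 0.5% to 42% range comes wholly from assumed inputs, and its upper end combines the two highest values. A reader might take 42%, or the 55 skin events, as an estimate of harm; the documents support neither use.

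A reader might also infer an effect on the primary safety endpoint. None is claimed: the gap concerns whether treatment may restart after the event.

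**What to change.** 1. Add a bullet to the permanent-discontinuation lists in 8.1.1.1 and 8.1.1.2: *SJS or TEN, once diagnosed, any grade*. Cohort A1 inherits it through 8.1.1.3.
2. Change the algorithm pointer from Appendix 7 to Appendix 8 in 7.4.4, 8.1.3 and Section 9.

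A matching exclusion in 7.4.5.1 and 7.4.5.2 is optional, because the resume text already refers to Section 8.

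The cost is two bullets and three pointer corrections. No new clinical decision is needed, since the rule is the sponsor's own, and data collection, sample size and analysis do not change.
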